5.3 Preparation and Administration/Implantation of Investigational Device

The SimPull does not physically engage with the patient. The device utilizes an adjustable bar to facilitate the lateral transfer.

5.4 Subject Compliance Monitoring

The Research Coordinator will track patients through Ptrax.

5.5 Packaging and Labeling

The SimPull will be labeled with:

“CAUTION – Investigational Device. Limited by Federal (or United States) law to investigational use”

5.6 Receiving, Storage, Distribution and Return

The SimPull devices will be delivered to the Dock on the Mayo Clinic Hospital campus by The Patient Company. The devices will be stored in the cardiac catheterization and electrophysiology lab. Upon completion of the pilot study, the devices will be returned to The Patient Company.

5.6.1 Receipt of Investigational Devices

The SimPull devices will be delivered to the Mayo Clinic Hospital campus by The Patient Company. The devices currently reside at the Arizona State University Health Services building. Two SimPull devices will be delivered for the study pilot.

5.6.2 Storage

The SimPull devices will be stored in the cardiac catheterization and electrophysiology lab throughout the pilot study.

5.6.3 Distribution of Study Device

There will be two SimPull devices available for the purpose of the pilot study. Either device can be utilized for lateral patient transfers.

5.6.4 Return or Destruction of Study Device

At routine intervals and at the completion of the study, there will be a reconciliation of devices shipped, devices utilized, and devices remaining. This reconciliation will be logged on the Device Accountability form, signed and dated. Any discrepancies noted will be documented, the sponsor-investigator will be notified and an investigation will be conducted to determine the cause of the discrepancy. The SimPull devices will be returned to The Patient Company. The devices will be placed on the Mayo Clinic Hospital Dock for retrieval by The Patient Company.

5.6.5 Cleaning/Sterilization Procedures

- Cleaning of the SimPull using:
 - Oxivir Tb Wipes
 - Bleach Wipes
 - Observation of device for defects during process

Study Procedures

Schedule of Events

Study Activity
Determine if patient meets eligibility criteria
Consent the patient
Utilize the SimPull for lateral patient transfer
Clean the SimPull device
Complete RedCap Survey

6 Statistical Plan

6.1 Sample Size Determination

Power estimate for feasibility outcomes

A sample size of 50 per transfer type (current method vs. SimPull) is estimated to achieve greater than 99% power to reject the null hypothesis of no difference in time to transfer using a two-sided two-sample equal variance t-test, assuming a mean time for transfer of 7 minutes under the current method and 3 minutes using SimPull, a standard deviation in both groups of 3.5 minutes, and a significance level of 0.5. A sample size of 50 transfers per type is estimated to achieve greater than 99% power to reject the null hypothesis of no difference in number of staff using a two-sided two-sample equal variance t-test, assuming a mean of 5 staff involved in transfer under the current method and 2 staff using SimPull, a standard deviation in both groups of 0.5, and a significance level of 0.5.

6.2 Statistical Methods

Descriptive Statistics

Patient and transfer characteristics will be descriptively summarized by transfer type. Staff questionnaires will be descriptively summarized. The difference between transfer methods in time for transfer and number of staff involved in transfer will be tested using two-sample t-tests. A possible secondary analysis would test differences using a regression model adjusting for differences in patient or transfer characteristics. The difference between transfer methods in proportion of transfers following the OSHA mandate of no more than 35 lbs. lifted per staff member will be tested using a Chi-square or Fisher's exact test. A possible secondary analysis would test differences using a regression model adjusting for differences in patient characteristics. The paired differences in mean staff satisfaction scores and self-rated risk of injury scores will be tested using paired tests.

Primary Hypothesis:

SimPull lateral transfer device is a more efficient and safe method of lateral patient transfer than current methods of lateral transfer.

By recording patient weight and the number of clinicians engaged during manual transfers we can calculate the force needed by each individual. Example: Patient weight: 265 lbs., five clinicians: 53 lbs. per clinician (51% higher than the 35 lb. OSHA mandate). This data collection allows risk assessment of clinician injury during transfer in each location by

establishing weight pulled by clinicians and the number of transfers per day. Using this we can also forecast force required and risk of injury over time. Time to complete in seconds will be recorded for each lateral transfer.

Secondary Hypothesis:

Use of the SimPull device for lateral transfers will increase staff satisfaction and be a preferred method of lateral patient transfer.

Data collected pre and post SimPull implementation

- Employee Satisfaction
- Employee Perception of Injury Risk

Staff/Clinician Participant Survey:

Part 1 of Survey – Pre-Training

1. What is your preferred method for performing lateral patient transfers?
 - a. Manual, Assisted, Ceiling Lift, or Air Mattress
2. Do you feel at risk of injury performing lateral patient transfers?
 - a. No Risk, Minimal Risk, Neutral, Some Risk, High Risk
3. How likely do you feel you are to be injured during lateral patient transfer?
 - a. Not at all likely, Not Likely, Neutral, Likely, Very Likely
4. What type of injury do you think you would have during lateral transfers?
 - a. Open response
5. What preventative measures do you take to avoid injury during lateral transfers?
 - a. Open response
6. Are you satisfied with current lateral patient transfer methods?
 - a. Yes/No

Part 2 of Survey – Post Training

1. What is your preferred method for performing lateral patient transfers?
 - a. Manual, Assisted, Lift, or SimPull
2. Do you feel at risk of injury performing lateral patient transfers using the SimPull?
 - a. No Risk, Minimal Risk, Neutral, Some Risk, High Risk
3. How likely do you feel you are to be injured during lateral patient transfer using SimPull?
 - a. Not at all likely, Not Likely, Neutral, Likely, Very Likely
4. What type of injury do you think you would have during lateral transfer using SimPull?
 - a. Open response
5. What preventative measures do you take to avoid injury during lateral transfers using SimPull?
 - a. Open response
6. Are you satisfied with lateral patient transfer using SimPull?
 - a. Yes/No

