3.2 Primary Study Endpoints

Endpoint 1: Difference between transfer methods in time for transfer.

Endpoint 2: Difference between transfer methods in number of staff involved in transfer.

Endpoint 3: Difference between transfer methods in proportion of transfers following the OSHA mandate of no more than 35 lbs. lifted per staff member (lbs. lifter per staff member calculated as: weight of patient in lbs. divided by number of staff involved in transfer).

Endpoint 4: Paired difference in satisfaction scores (satisfaction with current transfer method and with SimPull) on staff questionnaires.

Endpoint 5: Paired difference in self-rated risk of injury (with current transfer method and with SimPull) on staff questionnaires.

4 Subject Selection, Enrollment and Withdrawal

Patient selection will be based on set inclusion and exclusion criteria of patients scheduled for procedures in the cardiac catheterization and electrophysiology procedural area. If the patient meets eligibility requirements, consent will be obtained using a written consent process. **The Principal Investigator and Co-Principal Investigator or study members** with recorded conflict of interest do not have consenting privileges and will not participate in the recruitment or consenting process. Using REDCap, the study team will enter data based off transfer observations. If patient consents and no IRB approved study member is available to perform the transfer, the patient will be excluded from the study. If the patient meets inclusion criteria, the clinical research coordinator will validate that a study member is present to transfer the patient prior to consent,. Enrollment will begin with the first 50 patients using the current method of transfer-followed by the pre-survey of staff. Staff will then receive training on the SimPull transfer device and the next enrolled 50 patients will be transferred with SimPull; followed by post-survey of staff. Study members are defined as employees (registered nurses and technicians) of Mayo Clinic assigned to the cardiac catheterization and electrophysiology procedural areas.

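### The t-tests for Endpoints 1 and 2 and the power statement treat 100 transfers as independent, although staff repeat across them and no per-transfer staff identifier is planned

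*Combined protocol and SAP*

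**What the plan says.** On the analysis of Endpoints 1 and 2, section 6.2 reads: "The difference between transfer methods in time for transfer and number of staff involved in transfer will be tested using two-sample t-tests". The only adjustment foreseen is an optional regression on patient or transfer characteristics. Staff or team is not named as a term in it.

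Section 6.1 gives the power: "A sample size of 50 per transfer type (current method vs. SimPull) is estimated to achieve greater than 99% power", "using a two-sided two-sample equal variance t-test". For time the inputs are "assuming a mean time for transfer of 7 minutes under the current method and 3 minutes using SimPull" and "a standard deviation in both groups of 3.5 minutes, and a significance level of 0.5". For staff count they are "assuming a mean of 5 staff involved in transfer under the current method and 2 staff using SimPull" and "a standard deviation in both groups of 0.5, and a significance level of 0.5".

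Section 4 says who performs the transfers: "Study members are defined as employees (registered nurses and technicians) of Mayo Clinic assigned to the cardiac catheterization and electrophysiology procedural areas". It also requires a study member to be available for the transfer, and it places device training between the two phases. Section 3.1 limits SimPull use to study members who have had hands-on education. Endpoints 4 and 5 in section 3.2 are paired across methods on staff questionnaires.

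For each transfer, section 6.2 mentions patient weight, number of clinicians and time in seconds. No section mentions who took part, a random staff effect, a cluster-robust variance or a design effect.

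**The concern.** A two-sample t-test takes its standard error from 100 independent observations. Here the patients are distinct but the staff are not. If some people or teams are consistently faster, or habitually call for more help, transfers that share staff are correlated. The t-test standard error is then not the right one in general.

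The primary objective (section 2.1) is to show greater efficiency, so the confidence interval for the time difference is a main product of the study. If staff identity is not recorded at the time of transfer, no later analysis can check whether the interval is too narrow, too wide or about right.

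**Working it through.** **Inputs from the plan.** n = 50 per method. Time: means 7 and 3 min, SD 3.5. Staff count: means 5 and 2, SD 0.5. The significance level is printed as 0.5 in both power statements. I used 0.05 and checked 0.5 as well.

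**The plan's own figure.**
- Time: SE = 3.5 x sqrt(2/50) = 0.70 min. Exact t power is 99.99% at 0.05 and above 99.99% at 0.5.
- Staff count: SE = 0.5 x sqrt(2/50) = 0.10. Power is about 100% at either level.
- The stated power of more than 99% reproduces. The printed 0.5 needs confirming, but it does not affect this point.

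**Repeat participation.** 50 x 5 + 50 x 2 = 350 staff places over 100 transfers. Unless the pool is very large, people recur.

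**Effect on the standard error.** The simplification is one staff cluster per transfer. Let K be the number of operators, m = 50/K the transfers per operator per method, ICC the share of variance due to operator, and r the correlation of an operator's effect between the two methods. K, ICC and r are assumptions. With balanced staffing:

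DE = 1 + (m(1 - r) - 1) x ICC, and SE = 0.70 x sqrt(DE).

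The approximate true type I error of the nominal 5% test is 2 x (1 - Phi(1.96/sqrt(DE))). For K = 10, so m = 5:

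| ICC | r | DE | SE (min) | type I error |
|---|---|---|---|---|
| 0.1 | 0 | 1.40 | 0.828 | 9.8% |
| 0.1 | 0.5 | 1.15 | 0.751 | 6.8% |
| 0.1 | 1 | 0.90 | 0.664 | 3.9% |
| 0.2 | 0 | 1.80 | 0.939 | 14.4% |
| 0.2 | 0.5 | 1.30 | 0.798 | 8.6% |
| 0.2 | 1 | 0.80 | 0.626 | 2.8% |

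At DE 1.80 the 95% half-width goes from 1.96 x 0.70 = 1.37 min to 1.96 x 0.939 = 1.84 min.

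**Simulation of the plain t-test** (20,000 runs per setting, nominal 5%, staff drawn at random within each phase):

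| Setting | ICC 0.1 | ICC 0.2 |
|---|---|---|
| 10 operators, same staff, stable effects | about 5% | about 5% |
| 10 operators, 60/40 mix shift | 5.6% | 5.6% |
| 10 operators, 70/30 mix shift | 6.8% | 8.7% |
| 10 operators, 80/20 mix shift | 9.3% | 13.6% |
| 20 operators, 80/20 mix shift | 7.1% | 9.3% |
| 10 operators, effects unrelated between phases | 11.1% | 16.7% |

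An 80/20 shift means that half the operators do 80% of one phase and 20% of the other.

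**Does modelling staff repair it?** With 10 operators and an uneven mix (600 runs), the plain test gave 9.5% and 14.8% at ICC 0.1 and 0.2. A random operator intercept gave 4.8% and 4.7%. With 5 different operators per phase and uncorrected Wald tests, the error was still about 7% (400 runs, with many convergence warnings), so a small-sample correction is needed.

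**Power under clustering, at 0.05.**
- Time: exact t power is 99.2% at an effective n of 30 and 98.97% at 29. The statement of more than 99% therefore holds up to DE = 50/30 = 1.67, about 1.7 (1.78 by normal theory).
- Time at DE 1.80 (K = 10, ICC 0.2, r = 0): power is still 98.9%, or 98.0% with cluster-based degrees of freedom.
- Staff count: by normal theory, power stays above 99% up to DE = (3/0.10)^2 / (1.96 + 2.326)^2 = 900/18.37, about 49.

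**The case against.** The strongest reply is that the documents lean towards the harmless case. Endpoints 4 and 5 are paired, and section 4 describes staff being trained and then moving on to the device phase, so the same people are expected in both phases. With stable effects and random staffing, the t-test keeps its 5% level. This stands, and it is why no direction can be asserted. It does not settle the matter. Section 3.1 makes device use conditional on training and study membership. Pairing on questionnaires says nothing about how often each person works in each phase. A person's speed with the manual method also need not carry over to a motorised device.

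A reader might infer more than the documents support:
- **That the staff pool is small.** No number of staff is given.
- **That the intervals are wrong, or too narrow.** The sign depends on the ICC, the overlap of staff and the carry-over of their effects, none of which is stated.
- **That the study is underpowered.** The planned effect is large, and the power conclusion is robust.
- **That one lead operator per transfer is the natural cluster.** The plan defines no lead and assumes teams of 5 and 2. Endpoint 2 is itself a property of the team, so clustering by individual is less direct there.
- **That Endpoint 3 needs a cluster bootstrap.** With 2 staff, the 35 lb rule is met only up to 2 x 35 = 70 lb, against an average patient weight near 200 lb in section 1.1. The SimPull proportion would be close to zero, and resampling would show almost no variation.

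It is also fair to say that clustering is not the main limitation of a non-randomised before/after pilot. Modelling staff leaves confounding by period untouched.

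**Conclusion.** The point holds in a limited form. Sections 6.1 and 6.2 assume independence that the design does not guarantee, and the plan collects nothing that would let anyone check. What is in question is the validity of the p-values and intervals, chiefly for Endpoint 1, and not the sample size.

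Under assumed values of 10 to 20 operators and ICC 0.1 to 0.2, the true level of a nominal 5% test is roughly 7% to 17% after a marked shift in staff mix or with unrelated staff effects. It is about 5% with the same staff, stable effects and random staffing, and about 3% to 4% with a balanced mix (10 operators). At the planned 4 min difference, none of these cases would by itself overturn a finding for time. They would change the width of the reported interval. This is a cheap improvement, worth making before enrolment because the missing item cannot be recovered afterwards.

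**What to change.** 1. **Transfer record.** Add to each REDCap transfer entry the coded IDs of all staff taking part. One ID per transfer would not support a model for overlapping teams.
2. **Section 6.2.** For Endpoint 1, prespecify a staff-clustered estimate of the difference between methods with a 95% CI, reported beside the t-test. Use a mixed model with staff effects (crossed or multiple-membership if teams overlap) or cluster-robust standard errors. Name a small-sample correction in either case. Give the same analysis for Endpoint 2 as supportive only.
3. **Section 6.1.** State that the power assumes independent transfers, that more than 99% for time holds up to a design effect of about 1.7, and that the staff-count power is not at risk.

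The cost is one more data item per transfer and a few lines of text, with no extra patients. Intervals may be somewhat wider than from the t-test. The change does not remove period confounding, and the report should say so.

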5.2 Method for Assigning Subjects to Treatment Groups

Patient selection will be based on set inclusion and exclusion criteria of patients scheduled for procedure in the cardiac catheterization and electrophysiology procedural area. If the patient meets eligibility requirements, consent will be obtained using a paper consent process.

Patients will not be randomly assigned to treatment group. The first 50 patients (or greater than 50 if there are withdrawals) will have the current method of transfer. The next 50 patients (or greater than 50 if there are withdrawals) will have the SimPull device for transfer.

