11.3 Subject Stipends or Payments

No payments or reimbursements will be distributed in exchange for participation in this study.

12 Publication Plan

The data will be published in one report but as unique locations, allowing analysis of unique benefit or drawback in a specific location, aiming to prove feasibility in each.

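### Sequential, non-randomised groups, but only unadjusted t-tests are committed for time and staff number: adjust the primary estimate for patient weight, which is already recorded

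*Combined protocol and SAP*

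**What the plan says.** Section 5.2 states: "Patients will not be randomly assigned to treatment group". Section 4 gives the order: "Enrollment will begin with the first 50 patients using the current method of transfer". Staff are then trained, and the next 50 enrolled patients are moved with SimPull.

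For Endpoints 1 and 2, Section 6.2 commits to this: "The difference between transfer methods in time for transfer and number of staff involved in transfer will be tested using two-sample t-tests". It also commits to a description of the groups: "Patient and transfer characteristics will be descriptively summarized by transfer type". Adjustment is left open: "A possible secondary analysis would test differences using a regression model adjusting for differences in patient or transfer characteristics". Section 6.2 has a similar optional sentence, limited to patient characteristics, for Endpoint 3 (the share of transfers within 35 lb per staff member). Nowhere do the documents give a covariate list, a selection rule or a condition that would trigger adjustment.

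Weight is collected. Section 6.2 begins its explanation of force per clinician with "By recording patient weight and the number of clinicians engaged during manual transfers", and Endpoint 3 in Section 3.2 divides patient weight by number of staff. Whether the lab (catheterisation or electrophysiology) is recorded is less clear. Section 6.2 speaks of risk in each location, and the publication plan (Section 12) says "The data will be published in one report but as unique locations", but neither defines location as one lab or the other.

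**The concern.** Without randomisation, the raw difference in means combines the device effect with any systematic change in patients or setting between the two phases. If the SimPull phase had lighter patients, or a different mix of the two labs, part of the difference in time or staff would belong to that change. The descriptive table would show the imbalance, but the committed estimate would keep it. Because the regression is optional and unspecified, both the decision to run it and the choice of covariates could be made after seeing the data.

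This bears on the primary objective (Section 2.1), which is to show that SimPull is more efficient than current methods. What is at stake is how far the reported size of the effect can be trusted, since that is the figure a later study would use.

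**Working it through.** **Inputs from Section 6.1.** 50 transfers per method. Time: "assuming a mean time for transfer of 7 minutes under the current method and 3 minutes using SimPull", SD 3.5 minutes, so a planned difference of 4 minutes. Staff: 5 against 2, SD 0.5, so a planned difference of 3. The significance level is printed as 0.5; I use 0.05 and check both for the plan's own figure.

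**The plan's own figure.** SE for time = 3.5 × √(2/50) = 0.70 min, and 4/0.70 = 5.71. Noncentral t power with 98 df is 99.99% at alpha 0.05 and above 99.99% at 0.5. SE for staff = 0.5 × √(2/50) = 0.10, and 3/0.10 = 30, so power is about 100%. The stated power above 99% reproduces at either level.

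**Assumed inputs.** The documents give no weight–time correlation, lab effect or expected shift, so the following are assumptions about a systematic shift. Chance imbalance is already covered by the t-test's alpha. Each source is taken alone, and the bias can go either way.

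*Weight.* Bias = r × d × SD, where r is the within-group correlation of weight with the outcome (0.3 to 0.5) and d is the standardised weight difference between phases (0.2 to 0.5).
- Time: 0.3 × 0.2 × 3.5 = 0.21 min, to 0.5 × 0.5 × 3.5 = 0.875 min.
- Staff: 0.3 × 0.2 × 0.5 = 0.03, to 0.5 × 0.5 × 0.5 = 0.125.

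*Lab mix.* Bias = lab effect × difference in lab share between phases (10 to 40 percentage points).
- Time, lab effect 1 to 2 min: 1 × 0.10 = 0.1 min, to 2 × 0.40 = 0.8 min. Middle case: 2 × 0.20 = 0.4 min.
- Staff, lab effect 0.25 to 0.5: 0.25 × 0.10 = 0.025, to 0.5 × 0.40 = 0.2.

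**Consequences for time** (t-test, SE 0.70, 98 df, alpha 0.05):

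| Bias (min) | Share of planned 4 min | Rejection rate if no true effect | Power if true effect is 4 min and bias is against SimPull |
|---|---|---|---|
| 0.1 | 2.5% | 5.2% | 99.98% |
| 0.4 | 10% | 8.7% | 99.9% |
| 0.8 | 20% | 20.5% | 99.5% |
| 0.875 | 22% | 23.6% | 99.3% |

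In simulations of the lab-shift cases, regression on method, weight and lab with HC3 standard errors kept the rejection rate at 4.4% to 4.5%. In the 0.8-minute case it returned a mean estimate of 4.00, where the t-test gave 4.80 (or 3.20 with the bias reversed).

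**Consequences for staff.** A bias of 0.025 to 0.2 is 0.8% to 6.7% of the planned 3.

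**Power of the adjusted analysis for time.** With one covariate, d = 0.5 and no gain in precision (r = 0), the variance inflation is 1 + 0.5²/4 = 1.0625. SE is then 0.70 × √1.0625 = 0.722, and power with 97 df is 99.98%. In a harsher case the covariates explain 25% of group membership: SE = 0.70/√0.75 = 0.808, 95 df, power about 99.8%.

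**Endpoint 3.** With five staff, a transfer complies when weight is at most 5 × 35 = 175 lb. Take a normal weight distribution with mean 200 lb (Section 1.1 says nearly 200) and an assumed SD of 35 to 55 lb. At SD 35, compliance is 23.8%, rising to 28.4% if the mean is 5 lb lower and 33.4% if it is 10 lb lower. At SD 55, the figures are 32.5%, 35.8% and 39.3%. A 5 to 10 lb difference in mean weight therefore moves compliance under the current method by about 3 to 10 percentage points.

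**The case against.** The strongest reply is that the plan already foresees adjustment, commits to describing the groups, and fixes its main test in advance. On that view the gap is one optional word and a missing covariate list in a secondary analysis of a single-site pilot. Both phases share the site, procedural areas and eligibility rules, and enrolment is expected to take two months, so a large shift is not obvious. The upper figures need a 40-point change in lab mix with a 2-minute lab effect, or a half-SD weight shift with a correlation of 0.5. The top staff figure assumes a lab effect of one full SD.

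Much of this stands. Every size above is assumed. The fixed t-test also limits analyst freedom: a regression chosen later could not replace it without departing from the plan. But fixing an unadjusted test does not correct it. Followed as written, the plan leaves the estimate for its primary objective uncorrected for a variable it already collects.

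A shift is possible under the protocol's own rules, though not shown. Only trained study members may use SimPull, patients without an available study member are excluded, and two devices serve the catheterisation and electrophysiology areas.

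A reader might infer three stronger things that the documents do not support:
- *That the result would be wrong or lose significance.* The table shows that the planned effect survives the largest assumed bias. The rejection rates matter only if SimPull had no effect.
- *That regression would make the comparison as good as randomised.* Period, training and learning change exactly when the method changes, so no covariate can separate them.
- *That lab is certainly a recorded field.* This is only inferred from the references to location, and the device storage sections refer to a single combined lab. Weight is the only covariate the documents clearly secure.

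**Conclusion.** The concern holds in limited form. Allocation is sequential and non-randomised, the only committed tests for Endpoints 1 and 2 are unadjusted, and adjustment is optional with no covariates named. The committed estimates are therefore not corrected for measured imbalance in patient weight.

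Under the assumed shifts, the time estimate could move by about 0.1 to 0.9 minutes against 4, and the staff estimate by about 0.03 to 0.2 against 3. These ranges rest on assumed correlations, lab effects and shifts, on alpha 0.05, and on one transfer per patient. The size of the estimate is at risk; its significance very probably is not. The change is worth making because it is cheap.

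**What to change.** In Section 6.2, replace the optional regression sentence for time and staff number with:

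> The difference between transfer methods in time and in number of staff will be estimated by linear regression on transfer method, adjusted for patient weight, and for lab (cath/EP) if it is recorded, with robust standard errors. This is the primary estimate; the unadjusted two-sample t-test will be reported alongside. If more than one transfer per patient is analysed, transfer direction will be added and standard errors clustered by patient. Period, training and learning coincide with transfer method and cannot be removed by adjustment.

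The clustering clause is needed because Section 4.1 names transfers in both directions and the plan does not say whether one patient can contribute both.

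For Endpoint 3, keep the Chi-square or Fisher's exact test, show the weight distribution by method beside it, and commit to the weight-adjusted regression as a secondary analysis.

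Cost: a wording change and no added patients. With one transfer per patient, residual degrees of freedom fall from 98 to 97 with weight, and to 96 with lab as well. A further term for direction would make three degrees of freedom in all (95), although with repeated transfers the number of patients governs the clustered errors. Power for the planned 4 minutes at alpha 0.05 stays above 99%. If lab is not yet recorded, adding it needs one data field; otherwise adjust for weight alone. The model is slightly harder to explain than a t-test.
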